5.4 Primary Endpoints

The safety and tolerability of MEDI-546 will be assessed primarily by summarizing treatment-emergent AEs and SAEs and by assessing changes in viral cultures, including oropharyngeal swabs for HSV-1 and HSV-2; vaginal swabs for HSV-1, HSV-2, and HPV; and peripheral blood test for EBV and CMV (using molecular assays). The occurrence of treatment-emergent AEs and SAEs will be summarized from the period immediately following the first administration of MEDI-546 through end of study (Study Day 84 for subjects receiving single IV doses and Study Day 105 for subjects receiving multiple IV doses). Treatment-emergent AEs and SAEs will be summarized by system organ class and

preferred terms, by severity, and by relationship to MEDI-546. Treatment-emergent AEs and SAEs will be summarized for each of the MEDI-546 dose cohorts, and for all MEDI-546 dose cohorts combined.

No formal statistical testing will be performed to compare treatment groups. Other variables used for the safety assessments include serum chemistry, CBC with differential and platelets, and urinalysis. These variables as well as their changes from baseline will be summarized descriptively.

5.5 Secondary Endpoints

The secondary endpoints of the study are to assess the PK, IM, and PD of single and multiple IV doses of MEDI-546 in adult subjects with scleroderma.

5.5.1 Pharmacokinetics

Serum MEDI-546 concentration data will be tabulated by dose cohort together with descriptive statistics. Individual and mean serum concentration-time profiles of MEDI-546 by dose cohort will be generated and included in the report. Noncompartmental PK data analysis will be performed using the software package WinNonlin[®]. For PK data analysis, time zero is defined as the end of infusion. The PK parameters to be obtained and reported include, but are not limited to:

- C_{\max} - the maximum observed serum concentration of MEDI-546 following IV infusion
- T_{\max} - the time of the observed C_{\max}
- $AUC_{0-\infty}$ - the area under the serum concentration - time curve from time zero to infinity;
- AUC_{0-t} - the area under the serum concentration – time profile from time zero to the last measurable time point
- AUC_{0-7d} - the area under the serum concentration – time profile from time zero to 7 days post dose (for Dose Cohorts 6-8)
- $t_{1/2}$ - the terminal elimination half-life;
- CL - systemic clearance;

Descriptive statistics of noncompartmental PK parameters by dose cohort will be provided in the report. If the data allow, compartmental modeling may be performed to further

characterize the PK and the PK-PD relationship of MEDI-546 in scleroderma subjects. However, due to the exploratory nature of the study, the actual modeling work may not be reported.

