MEDI-546 will be administered as an IV infusion over at least 60 minutes for IV doses of ≤ 10 mg/kg or at least 120 minutes for doses of > 10 mg/kg. For doses > 10 mg/kg and for subjects weighing > 250 lbs. or 114 kg please call the medical monitor to discuss the infusion rate instructions. Single IV dose administration will occur on Study Day 0, with follow-up through Study Day 84; multiple-dose IV administration of MEDI-546 will occur on Study Days 0, 7, 14, and 21, with follow-up through Study Day 105.

On [REDACTED], an interim analysis of PK and type 1 IFN gene signature from all subjects through Day 14 of Cohort 4 (Dose Cohorts 1-4) was performed as described in Section 5.7 of the study protocol. Results of this analysis are summarized in Section 1.4 of the study protocol.

Subject Evaluation and Follow-up:

Screening evaluations will be performed within 28 days prior to MEDI-546 administration. Safety evaluations will be performed from the time the informed consent is signed through end of study and will include history and physical examinations, assessment of adverse events (AEs) and serious adverse events (SAEs), monitoring of laboratory tests including hematology, serum chemistry, and urinalysis, safety biomarkers in any subject who has a Grade 1 or higher infusion reaction (including serum levels of mast cell tryptase,

cytokines/chemokines, and IgE antibodies), and viral monitoring. Pharmacokinetics, IM, and receptor occupancy will be assessed throughout the study. Receptor occupancy and level of type I IFN gene signature in whole blood and skin will be determined to assess the PD effect of MEDI-546. Clinical outcomes will be evaluated.

The schedule of subject evaluations for subjects receiving single IV doses of MEDI-546 (Dose Cohorts 1-5 and 9) is presented in [Table 3.5-1](#); the schedule of subject evaluations for subjects receiving multiple IV doses of MEDI-546 (Dose Cohorts 6-8) is presented in [Table 3.5-2](#).

Sample Size and Power Calculations:

A minimum of 33 subjects are planned for this study, with dose cohorts of subjects receiving 1 of 6 single IV doses followed by 3 cohorts of subjects receiving 1 of 3 multiple IV doses of MEDI-546; the final single dose cohort 9 (20 mg/kg) will enroll simultaneously to Cohorts 6, 7, and 8 as follows:

- Dose Cohort 1 (N=1): 0.1 mg/kg MEDI-546 as a single IV dose
- Dose Cohort 2 (N=4): 0.3 mg/kg MEDI-546 as a single IV dose
- Dose Cohort 3 (N=4): 1.0 mg/kg MEDI-546 as a single IV dose

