3.4.2 Treatment Regimens

A minimum of 33 evaluable subjects are planned for the study, with cohorts of subjects receiving 1 of 5 single IV doses followed by 3 cohorts of subjects receiving 1 of 3 multiple IV doses of MEDI-546 as shown in [Table 3.4.2-1](#); an additional single-dose cohort (Dose Cohort 9, 20 mg/kg) will enroll simultaneous to Cohort 6, 7, and 8. MEDI-546 will be administered as an IV infusion over at least 60 minutes for IV doses of ≤ 10 mg/kg or at least 120 minutes for IV doses of > 10 mg/kg. For doses > 10 mg/kg and for subjects weighing > 250 lbs. or 114 kg please call the medical monitor to discuss the infusion rate instructions.. Single-dose IV administration of MEDI-546 will occur on Study Day 0, with follow-up through Study Day 84; multiple-dose IV administration of MEDI-546 will occur on Study Days 0, 7, 14, and 21, with follow-up through Study Day 105.

Table 3.4.2-1 Treatment Regimens

Dose Cohort	Number of Subjects^a	MEDI-546 Treatment^b
1	1	0.1 mg/kg MEDI-546 as a single IV dose
2	4	0.3 mg/kg MEDI-546 as a single IV dose
3	4	1.0 mg/kg MEDI-546 as a single IV dose
4	4	3.0 mg/kg MEDI-546 as a single IV dose
5	4	10.0 mg/kg MEDI-546 as a single IV dose
6	4	0.3 mg/kg MEDI-546 as a weekly IV dose x 4 doses
7	4	1.0 mg/kg MEDI-546 as a weekly IV dose x 4 doses
8	4	5.0 mg/kg MEDI-546 as a weekly IV dose x 4 doses
9	4	20 mg/kg MEDI-546 as a single IV dose

^a Each dose cohort may be expanded by 2 additional subjects if the eligible subjects are already in screening at the time that enrollment into that cohort has been completed and there is no possible safety signal to warrant expansion of the dose cohort to a maximum of 8 subjects.

^b Dose levels for Dose Cohorts 6-8 may be modified based on possible interim analyses.

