Infusion reactions have been reported with the administration of intravenous gammaglobulin and nearly all approved monoclonal antibodies. For purposes of this protocol, infusion reactions are defined as anaphylactoid-like AEs related to the infusion of the investigational product itself that usually occur within the first 24 hours after infusion, especially within minutes to a few hours, and will be distinguished from true anaphylactic reactions by absence of measurable antibodies against the investigational product. Infusion reactions are characterized by a complex of signs and symptoms that include flu-like illness, fever, chills/rigors, nausea, urticaria, headache, bronchospasm, angioedema, hypotension, hypoxia, pulmonary infiltrates, acute respiratory distress syndrome, myocardial infarction, ventricular fibrillation, and cardiogenic shock. For purposes of this protocol, a classification of infusion reactions is given in [Table 3.4.4-1](#), with suggested treatment options. Final treatment is at the discretion of the investigator and should reflect local standard of care.

Table 3.4.4-1 Classification and Suggested Treatments for Infusion Reactions

Severity of Symptoms	Treatment	Study Drug

Mild (Grade 1)
 
Localized cutaneous reactions such as mild pruritus, flushing, rash, dizziness, headache, ≤ 20 point change in systolic BP
	
 • Stop study drug infusion immediately • Evaluate patient, including close monitoring of vital signs • At the discretion of the investigator, treat patient, for example with 
 – Normal saline (~500-1000 mL/hour IV) – Diphenhydramine 50 mg IV – Acetaminophen 500-650 mg 	
 • Option 1: Do not resume infusion; OR, at the discretion of the investigator, resume current infusion under observation and complete study drug infusion at no more than half the planned infusion rate • Option 2: Discontinue further administration of study drug ;OR, at the discretion of the investigator, continue study drug administration and consider slowing infusion rate and pretreating patient 1.5-0.5 hours prior to study drug administration, for example with 
 – Diphenhydramine 50 mg IV – Acetaminophen 500-650 mg

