3.6.14 Pharmacokinetic and Pharmacodynamic Evaluations

The following PK and PD assessments will be made during the study:

- Serum will be collected at every study visit for the determination of MEDI-546 serum concentration. On Study Day 0 for both single- and multiple-dose administration and on Study Day 21 for multiple dose administration, PK sampling will occur pre-dose and at 0.5 hour post end of infusion. Specific procedures for sample collection, processing, storage, and shipment can be found in a separate laboratory manual provided to sites.
- Whole blood will be collected at visits specified in the study schedule ([Table 3.5-1](#) and [Table 3.5-2](#)) to measure the level of receptor occupancy (flow cytometry measurement of the binding of labeled MEDI-546 in the presence of dosed levels of MEDI-546) and total IFNAR levels (using a separate anti-IFNAR1 antibody that binds to a distinct epitope from MEDI-546). On Study Day 0 for both single- and multiple-dose administration and on Study Day 21 for multiple dose administration, receptor occupancy sampling will occur pre-dose and at 0.5 hour post end of infusion. Specific procedures for sample collection, processing, storage, and shipment can be found in a separate laboratory manual provided to sites.
- Type I IFN-inducible genes also will be used to measure the PD of MEDI-546. Whole blood samples will be used to analyze the effects of MEDI-546 on levels of mRNA for type I IFN-inducible genes. This analysis is performed using Affymetrix whole genome expression array and taqMan-based assay on selected panel of genes. Whole blood will be collected at visits specified in the study schedule. Specific procedures for sample collection, processing, storage, and shipment can be found in a separate laboratory manual provided to sites.
- Skin biopsies will also be collected for type I IFN-inducible genes and exploratory studies. Baseline skin biopsy (one 6mm or two 3mm or two 4mm) should be obtained prior to MEDI-546 administration on Study Day 0 and can be obtained anytime between screening and MEDI-546 administration. Sites will be given specific instructions for sample collection, processing, storage, and shipment.

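### Setting PK time zero at the end of infusion drops the infusion from AUC and slightly overstates clearance

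*Protocol*

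**What the plan says.** Section 5.5.1 fixes the PK clock: "For PK data analysis, time zero is defined as the end of infusion". AUC0-inf is the area under the "curve from time zero to infinity", AUC0-t has the same starting point, and AUC0-7d runs "from time zero to 7 days post dose (for Dose Cohorts 6-8". Clearance is listed without a formula. Nothing in the section adds the infusion area back, and it does not say whether the 7 days are counted from the start or the end of the infusion.

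The Study Abstract gives the infusion time as "over at least 60 minutes for IV doses of ≤ 10 mg/kg or at least 120 minutes for doses of > 10 mg/kg". These are minimum times. After a Grade 1 or 2 infusion reaction, Table 3.4.4-1 in Section 3.4.4 lets the investigator "complete study drug infusion at no more than half the planned infusion rate", so an individual infusion can run longer.

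Weekly doses are given on Days 0, 7, 14 and 21. On Days 0 and 21, Section 3.6.14 says "PK sampling will occur pre-dose and at 0.5 hour post end of infusion". Table 3.5-2 makes the Day 7 and Day 14 samples pre-dose only. No sample is scheduled during an infusion.

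**The concern.** The whole dose enters the body between the start and the end of infusion. An AUC that begins at the end of infusion sets the full dose against only part of the exposure it produced. AUC is too low and dose/AUC too high, always in the same direction. The missing share depends on infusion length, which differs by design between 20 mg/kg and the lower doses and may differ between subjects, and on elimination rate. It is therefore not a constant that cancels when cohorts are set side by side.

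The same clock makes AUC0-7d ambiguous for dose 1 of the weekly cohorts. Seven days after the end of the first infusion is about the end of the second, while the last sample belonging to the interval is the Day 7 pre-dose one. The analyst must truncate, extrapolate or integrate into the next dose, and the protocol does not say which.

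PK is a secondary objective, so what is at stake is the accuracy of descriptive AUC and clearance values.

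**Working it through.** The protocol states no human AUC, clearance or half-life, so there is no figure to reproduce.

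**Inputs.** Infusion time T = 1 h (doses up to 10 mg/kg, including all weekly cohorts) or 2 h (20 mg/kg), both planned minima. Dosing interval 168 h. Half-life is an assumption, shown from 14 days to 1 day with shorter values as a stress case. Section 1.3 says only that it was under a week in most monkey dose groups.

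**Step 1: area lost from AUC0-inf.** One compartment, constant-rate infusion, k = ln 2 / half-life:

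- share of AUC0-inf before the end of infusion = 1 − (1 − e^(−kT))/(kT), roughly kT/2
- overstatement of dose/AUC = kT/(1 − e^(−kT)) − 1

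Example, half-life 24 h and T = 1 h: k = 0.6931/24 = 0.02888 per hour. (1 − e^(−0.02888))/0.02888 = 0.02847/0.02888 = 0.9857. The loss is 1.43%, and clearance is overstated by 1/0.9857 − 1 = 1.45%.

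| Half-life | Loss, T = 1 h | Clearance overstated, T = 1 h | Loss, T = 2 h | Clearance overstated, T = 2 h |
|---|---|---|---|---|
| 14 days | 0.10% | 0.10% | 0.21% | 0.21% |
| 7 days | 0.21% | 0.21% | 0.41% | 0.41% |
| 4 days | 0.36% | 0.36% | 0.72% | 0.72% |
| 2 days | 0.72% | 0.72% | 1.43% | 1.45% |
| 1 day | 1.43% | 1.45% | 2.83% | 2.92% |

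At T = 1 h the loss is 2.83% at a half-life of 12 h and 5.56% at 6 h. It passes 5% only below about 6.7 h. For an infusion slowed to 4 h, it is 0.8% at 7 days and 5.6% at 1 day.

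**Step 2: AUC0-7d, T = 1 h.** Change against a window that starts with the infusion and lasts 168 h:

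| Half-life | Dose 1, integrated through the next infusion | Dose 1, pre-dose decline extrapolated | Dose 1, stopped at 168 h after start | Dose 4 |
|---|---|---|---|---|
| 1 day | +0.02% | −1.42% | −1.44% | −1.43% |
| 2 days | +0.14% | −0.65% | −0.79% | −0.72% |
| 4 days | +0.31% | −0.21% | −0.51% | −0.36% |
| 7 days | +0.41% | 0.00% | −0.41% | −0.19% |
| 14 days | +0.50% | +0.15% | −0.35% | −0.07% |

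The dose 1 overlap is 1 h of 168 h (0.6%). Integrating through it adds exposure that offsets, or slightly exceeds, the omitted first hour. After dose 4 there is no overlap because no dose follows Day 21. Doses 2 and 3 have no post-infusion samples, so the question does not arise for them.

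**Step 3: the scheduled samples.** Noncompartmental AUC0-7d for dose 1 (linear up, log down; pre-dose, 0.5 h after infusion, Day 1, Day 7 pre-dose), error against the true area for half-lives of 1 to 14 days:

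- time zero at start: −0.7% to −0.2%
- time zero at end, concentration back-extrapolated to time zero: −1.4% to −0.35%
- time zero at end, pre-dose zero placed at time zero: −2.2% to −0.5%

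**Step 4: scale.** The Day 7 visit may move by a day either way. Ending the interval 24 h early or late without using actual times shifts AUC by −4.1% or +2.9% at a half-life of 2 days, and by −12.3% or +11.7% at 14 days. At 2 days and longer this exceeds the time-zero effect.

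**The case against.** The best defence is that this hardly matters. PK is descriptive, planned cohorts hold 1 or 4 subjects, and Section 5.5.1 plans no test that a shift of about 1% could distort. Nothing is sampled during the infusion, so that area is interpolated under either definition. On the scheduled samples, moving the clock gains under one percentage point when the starting concentration is back-extrapolated. Section 5.1 also announces an analysis plan, where actual times and starting concentrations could be handled. All of this stands as to size. It does not remove the point, because the protocol states the time-zero rule outright, and the rule as written drops the infusion.

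Three stronger readings are tempting but unsupported:

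- **The overlap with the second infusion lowers AUC0-7d further.** It does not. Integrated, it roughly cancels the loss. The Day 7 sample is pre-dose, so no data from the second infusion can enter the dose 1 window anyway.
- **Clearance could be off by 6% to 12%.** A 2 h infusion with a half-life of 12 h or 6 h gives 5.9% or 12.0%. But "at least 120 minutes for IV doses of > 10 mg/kg" applies only to the 20 mg/kg cohort, the highest dose. Under saturable clearance, the fast elimination needed would be expected at the lowest doses.
- **The protocol expects antigen-sink non-linearity in patients, which this bias would exaggerate.** Section 1.3 reports monkey AUC and attributes it jointly to an antigen sink and uneven anti-drug antibody formation. It states no expectation for humans.

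**Conclusion.** The point holds as a minor defect in a stated rule. AUC0-inf and AUC0-t omit the infusion, and dose/AUC overstates clearance. At the minimum infusion times and half-lives of 1 to 14 days, the AUC0-inf loss is 0.1% to 1.4% for 1 h and 0.2% to 2.8% for 2 h. The dose 1 AUC0-7d has a nominal end about one infusion length past its last usable sample, which is a mismatch of definition and not a second bias.

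The figures assume one compartment, a constant infusion rate and clearance computed as dose/AUC. Section 1.3 describes biphasic disposition in monkeys. If that holds in patients, the k in kT/2 is clearance over central volume, which exceeds the terminal rate constant, so the loss would be larger than the table shows for a given terminal half-life. If that rate were twice the terminal one, for example, the loss would roughly double. Because no human half-life is given, very fast elimination at the lowest doses cannot be excluded, but nothing in the protocol supports the half-life below 6.7 h needed for a 5% loss at 1 h. The primary objective and the sample size are untouched.

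**What to change.** In Section 5.5.1, define time zero as the start of infusion. State that the noncompartmental analysis uses actual sampling times and each subject's recorded infusion duration. Define AUC0-7d for dose 1 in Cohorts 6-8 as 0 to 168 h from the start of infusion, closed on the Day 7 pre-dose sample and interpolated or scaled to 168 h by its actual time. For dose 4, use the same 168 h interval from the start of the Day 21 infusion. Using actual times also deals with the visit window, which can matter more than the time-zero choice.

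The cost is a sentence or two of text, plus carrying infusion start and stop times into the PK dataset. No sample, visit or dosing instruction changes.

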5.5.2 Immunogenicity

The presence of anti-MEDI-546 antibodies in serum will be assessed. Immunogenicity test results will be available for safety review at approximately 2-month intervals, with assays to be run after the first three cohorts have completed Study Day 28 and about every 2 months thereafter. Immunogenicity results will be analyzed by summarizing the number and percentage of scleroderma subjects who develop detectable anti-MEDI-546 antibodies by treatment and dose cohort.

5.5.3 Pharmacodynamics

The level of receptor occupancy will be determined by flow cytometry as a measure of the binding of labeled MEDI-546 in the presence of dosed levels of MEDI-546. Total type I IFNAR levels will be assessed using a separate anti-IFNAR1 antibody that binds to a distinct epitope from MEDI-546.

The level of expression of type I IFN-inducible genes will be determined in whole blood and skin mRNA, using Affymetrix technology. Results will be listed by dose group with mean and individual results at different time points. Changes from baseline will be described and PD assessed. Relationships between receptor occupancy and inhibition of type I IFN gene signature will be explored.

5.6 Exploratory Endpoints

5.6.1 Effect of MEDI-546 on Disease Activity and Patient-reported Outcomes

Measures of disease activity will include pulmonary function tests (FVC and DL_{CO} as absolute value and percent predicted), mRTSS, and the European DAI. Patient-reported outcomes will include the HAQ-DI with scleroderma NRS scores ([Steen, 1997](#); [Appendix 2](#)), and DAI with a numeric rating scale to assess changes in skin, changes in vascular manifestations, and changes in heart/lung. The mRTSS, European DAI, and the HAQ-DI with scleroderma NRS will be computed. These measures of disease activity, as well as their

respective changes from baseline, will be summarized descriptively at each visit by dose cohort and all cohorts combined.

5.6.2 Effect of MEDI-546 on Gene and/or Protein Expression

The effect of MEDI-546 on the expression of other genes and/or proteins in whole blood, serum, skin and on immunohistopathology of the skin will be assessed using descriptive statistics. These will include expression of collagen I and III genes and proteins in skin and the N-terminal propeptide of procollagens I and III in serum.

5.6.3 Relationship of Type I IFN-related DNA Polymorphisms and Safety

Polymorphisms in type I IFN-related genes associated with safety signals to MEDI-546 may be assessed using descriptive statistics.

5.7 Interim Analyses

The following interim analyses may be conducted:

- Type I IFN gene expression will be assessed cumulatively in blood and skin after each Dose Cohort reaches Study Day 28.
- After all subjects in Dose Cohort 4 complete Study Day 14, an interim analysis of cumulative data on PK and type I IFN gene signatures may be completed to determine whether dose adjustments need to be made in the multiple dose cohorts (Dose Cohorts 6-8). Target doses for multiple IV dosing are to include one dose that provides incomplete inhibition of type I IFN gene signature defined as $\geq 70\%$ inhibition in < 3 patients per cohort, one dose that provides nearly complete inhibition of type I IFN gene signature defined as $\geq 70\%$ inhibition in at least 3 subjects per cohort, and one dose that is approximately $\frac{1}{2}$ log higher than the dose that provides nearly complete inhibition of type I IFN gene signature in the skin.

6 Data Collection and Monitoring

The study will be monitored by MedImmune or its designee on a regular basis throughout the study period. During monitoring visits, the investigator or designee will provide direct access to all source documentation relevant to the subject's participation in the study. Source documentation includes, but is not limited to, the subject's clinic and/or office chart, hospital chart, informed consent forms, treatment notes, laboratory reports, pharmacy records, radiographs, and any other records maintained to conduct and evaluate the clinical study. The investigator must also ensure that direct access to study documents be made available for study-related audits, IRB/IEC review, or regulatory inspection.

Data recorded on source documents will be transcribed onto a validated data collection instrument (a paper case report form or electronic data screen) provided by MedImmune or designee. The investigator must ensure the accuracy and completeness of the data reported, and its consistency with the source documentation.

Data will be collected on all subjects who provide written informed consent. For subjects who fail the screening process, the following data will be collected:

- 1) Subject demographics
- 2) The reason the subject was not entered (ie, did not meet one or more inclusion criteria, met one or more exclusion criteria, or other (eg, lost to follow-up, consent withdrawn))

The primary source document for this study will be the subject's medical record. If separate research records are maintained by the investigator(s), both the medical record and the research records will be monitored/audited for the purposes of the study.

Study documents (including subject records, copies of collected data, study notebook, and pharmacy records) must be kept secured in accordance with MedImmune policies and applicable regulatory requirements for a period of 2 years following marketing of MEDI-546 or for 2 years after sites have been notified that the IND has been discontinued. There may be other circumstances for which MedImmune is required to maintain study records and, therefore, MedImmune should be contacted prior to removing study records for any reason.

7 Human Subjects

